**Table 5 Schedule of Assessments in Study E7080-G000-230 – Randomization Phase**

Phase	Prerandomization		Randomization a (All cycles are 21 days in duration)																		
Period	Screening b	Baseline c	Treatment d																Off-Tx	Follow-up	
Visit	1	2	3	4	5	6	7	8	9	10	11	12	13	14	15	16	17	18+			
Cycle			Cycle 1			Cycle 2			Cycle 3			Cycle 4			Cycle 5			Cycle 6-X			
Day	-28 to -2	-1	1	8	15	1	8	15	1	8	15	1	8	15	1	8	15	1			
Procedures/Assessments																					

then the subject does not need a reassessment at the Off-treatment Visit. X-ray of only 1 leg is required, and if reassessment is needed at the Off-treatment Visit, the x-ray must be performed on the same leg as at Screening. Tibial growth plate x-rays will be optional for Germany. A dental examination by a qualified healthcare professional should be conducted per local institutional guidelines at baseline (C1D1±4 weeks), and thereafter per local standard of care (but no less than annually), and as part of the Off-treatment assessment. If the most recent dental examination is within 6 months prior to the Off-treatment Visit, the dental exam is not required. Post-baseline dental exams are not required for subjects for whom permanent teeth (excluding third molars) are evaluated to be fully erupted at baseline.

- t. Tanner Staging is only required for female subjects  $\geq 8$  years old, and male subjects  $\geq 9$  years old. Tanner Stage will be assessed at the Baseline Visit, at the Off-treatment Visit, and annually thereafter during the Post-treatment Follow-up. Tanner Staging is not required once pubertal development is complete (ie, Tanner Stage 5).
- u. Every effort should be made to administer the PedsQL questionnaires as soon as possible after the decision to discontinue study treatment is made.
- v. Optional blood samples may be collected only from subjects in Arm A at the Baseline Visit, C1D15, Day 1 of Cycles 2, 4, and 6, for assessment for blood serum sample to measure factors implicated in angiogenesis. Pharmacodynamic sampling should not be performed for any subject with a body weight  $< 16$  kg (please see [Section 9.5.1.3.1](#)).
- w. An archival tumor sample from the most recent surgery or biopsy for identification of predictive biomarkers and pathology review may be collected from subjects in Arm A at any time during the study, unless no such material is available. Providing archival tumor samples is optional and does not impact subject eligibility.
- x. Survival data will be collected every 3 months for up to 2 years as per the protocol. All anticancer therapies will be collected.
- y. Concomitant medications will be recorded throughout the study and for 30 days after last dose. All anticancer therapy will be recorded until time of death or termination of Survival Follow-up.
- z. All AEs, including SAEs will be recorded from the date of signed informed consent, throughout the study, and for 30 days after last dose. SAEs irrespective of relationship to study treatment must be reported as soon as possible but not later than 24 hours.

**Table 6** presents the Schedule of Procedures/Assessments for the Extension Phase of the study.

**Table 6 Schedule of Assessments in Study E7080-G000-230 – Extension Phase**

Phase	Extension a	
Period	Treatment Period a	Follow-up Period
Visit	98	99
Cycle	Cycle X +1 and beyond	Off-Tx Visit
Day	1	
Procedures/Assessments		
Pregnancy test b	X	X
Lansky play score/ Karnofsky PS c	X	X
Physical examination d	X	X
Vital signs e	X	X
12-lead ECG f	As clinically indicated	
Echocardiogram or MUGA scan g	As clinically indicated	
Clinical chemistry and hematology h	X	X
Urine dipstick testing i	X	X
Study treatment j	Arm A: Lenvatinib+ifosfamide+etoposide a Arm B: Ifosfamide + etoposide a	
Tumor assessments: CT/MRI k	After data cutoff for the primary analysis, tumor assessments may be performed as clinically indicated as per the institutional guidelines (but no less frequently than every 12 weeks), following the prevailing local standard of care.	
Brain CT/MRI l	After data cutoff for the primary analysis, tumor assessments may be performed as clinically indicated as per the institutional guidelines, following the prevailing local standard of care.	
Height m	To be checked every 4 cycles	X
Tanner Stage n		X
HRQoL o	X	X
Proximal Tibial growth plate x-ray p		X
Dental examinations q	X	X
Survival r	X	X
Concomitant medications s	Throughout	X
AEs/SAEs t	Throughout	X

AE = adverse event, CT = computerized tomography, ECG = electrocardiogram, HRQoL = Health-Related Quality of Life, ICL = imaging core laboratory, MRI = magnetic resonance imaging, MUGA = multiple-gated acquisition, PD = disease progression, PS = performance status, SAE = serious adverse event.

- a. In the Treatment Period, subjects still on study treatment following the completion of the Randomization Phase will continue to receive study treatment as outlined in [Section 9.1.2.1](#) until disease progression, development of unacceptable toxicity, subject request, withdrawal of consent, or discontinuation of study by the sponsor, whichever occurs first.
- b. A serum or urine pregnancy test will be performed on Day 1 of each cycle and at the Off-treatment Visit in women of childbearing potential.
- c. A Lansky play score or Karnofsky performance status score will be obtained at Day 1 of every cycle visit.
- d. A physical examination will be performed at Day 1 visit of each cycle, and at the Off-treatment Visit. A

**Table 6 Schedule of Assessments in Study E7080-G000-230 – Extension Phase**

Phase	Extension a	
Period	Treatment Period a	
Visit	98	99
Cycle	Cycle X +1 and beyond	Off-Tx Visit
Day	1	

symptom-directed physical examination will be performed at any time as clinically indicated.

- e. Assessments will include vital signs (resting BP, HR, RR, and body temperature), and weight. Blood pressure that is consistently above the 95th percentile for sex, age, and height/length for subjects <18 years old; or BP  $\geq$ 140/90 mmHg for subjects  $\geq$ 18 to 25 years old requires further evaluation. Refer to hypertension management guidelines in [Section 9.4.1.1.2](#).
- f. Single 12-lead ECG. Subjects must be in the recumbent position for a period of 5 minutes prior to the ECG.
- g. An echocardiogram or MUGA scan is to be performed as clinically indicated.
- h. Clinical chemistry and hematology results must be reviewed within 48 hours after administering any study drug for all subsequent cycles. Electrolytes such as potassium, calcium, and magnesium should be monitored and abnormalities, when considered clinically significant, should be corrected in all participants before starting treatment. Scheduled assessments may be performed within 72 hours prior to the visit. If  $\geq$ Grade 3 hematologic or clinical chemistry toxicity, repeat laboratory test and AEs assessment at least every 3 days (until improvement to <Grade 3). TSH should be assessed for all subjects.
- i. Urine dipstick testing should be performed on Day 1 of every cycle, or more frequently as clinically indicated, and at the Off-treatment Visit. For subjects with a history of proteinuria  $\geq$ 2+, urine dipstick testing should be performed until the results have been 1+ or negative for 2 consecutive cycles. If a new event of proteinuria  $\geq$ 2+ occurs, refer to [Section 9.4.1.1.4](#) for further management guidelines. Urine glucose should be performed as part of the urine dipstick.
- j. Subjects randomized to Arm A will continue to receive lenvatinib only until progressive disease, unacceptable toxicity, or withdrawal of consent.
- k. After data cutoff for the primary analysis, tumor assessments may be performed as clinically indicated as per the institutional guidelines (but no less frequently than every 12 weeks), following the prevailing local standard of care. The scans will no longer be required to be sent to the ICL.
- l. Brain CT with contrast or MRI pre- and post- gadolinium contrast will be performed as per the institutional guidelines, following the prevailing local standard of care.
- m. Height will be assessed at the Baseline Visit, Day 1 of every 4 cycles during the Treatment Phase, at the Off-treatment Visit and every 3 months during the Post-treatment Follow-up. Assessment of height in Post-treatment Follow-up is not required once pubertal development is complete.
- n. Tanner Staging is only required for female subjects  $\geq$ 8 years old and male subjects  $\geq$ 9 years old. Tanner Stage will be assessed at the Baseline Visit, at the Off-treatment Visit, and annually thereafter during the Post-treatment Follow-up. Tanner Staging is not required once pubertal development is complete (i.e., Tanner Stage 5).
- o. HRQoL will be collected at week 18 and the Off-Treatment visit. Every effort should be made to administer the PedsQL questionnaires as soon as possible after the decision to discontinue study treatment is made.
- p. Proximal tibial growth plate x-rays should be conducted for subjects aged <18 years at baseline and at the Off-treatment Visit. If the growth plates are closed at baseline then the subject does not need a reassessment at the Off-treatment Visit. X-ray of only 1 leg is required, and if reassessment is needed at the Off-treatment Visit, the x-ray must be performed on the same leg as at Screening. Tibial growth plate x-rays will be optional for Germany.
- q. A dental examination by a qualified healthcare professional should be conducted per local institutional guidelines at baseline (C1D1 $\pm$ 4 weeks), and thereafter per local standard of care (but no less than annually), and as part of the Off-treatment assessment. If the most recent dental examination is within 6 months prior to the Off-treatment Visit, the dental exam is not required. Post-baseline dental exams are not required for subjects for whom permanent teeth (excluding third molars) are evaluated to be fully erupted at baseline.

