#### 9.4.1.1.11 MANAGEMENT GUIDELINES FOR QT PROLONGATION

Lenvatinib should be withheld in the event of development of QT interval prolongation greater than 500 msec. Lenvatinib should be resumed at a reduced dose when QTc prolongation is resolved to  $< 480$  msec or baseline. Monitor potassium, calcium and magnesium, and replenish as appropriate.

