#### 9.5.1.4.6 ELECTROCARDIOGRAMS

Electrocardiograms will be obtained as designated in the Schedule of Assessments ([Table 5](#) and [Table 6](#)). Complete, standardized, 12-lead ECG recordings that permit all 12 leads to be displayed on a single page with an accompanying lead II rhythm strip below the customary 3×4 lead format are to be used. In addition to a rhythm strip, a minimum of 3 full complexes should be recorded from each lead simultaneously. If possible, subjects must be in the recumbent position for a period of 5 minutes prior to the ECG.

QTc prolongation has been seen in some lenvatinib studies. Monitor ECGs every cycle (as specified in the Schedule of Assessments) in participants with congenital long QT syndrome, congestive heart failure, bradyarrhythmias, or those who are taking drugs known to prolong the QT interval, including Class Ia and III antiarrhythmics. Drugs known to prolong the QTc interval (including Class Ia and III antiarrhythmics) must be used cautiously. Please refer to the lenvatinib IB or lenvatinib prescribing information.

An ECG abnormality may meet the criteria of an AE as described in this protocol (see [Section 9.5.1.4.1](#)) and the CRF Completion Guidelines. In these instances, the AE corresponding to the ECG abnormality will be recorded on the Adverse Events CRF.

For ECG abnormalities meeting criteria of an SAE (see Serious Adverse Events and Other Events of Interest), the study site must fax the SAE report including the ECG report to the number indicated in the Investigator File using the SAE reporting form (see [Section 9.5.4.1](#)).

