##### **Echocardiogram or Multigated Acquisition (MUGA) Scan**

An echocardiogram or MUGA scan to assess LVEF will be performed during the screening phase, every 16±2 weeks following the first dose of study drug while the subject is on treatment or sooner, if clinically indicated, and at (or within 1 week following) the off-treatment assessment. LVEFs as assessed by the institution will be entered onto the CRF. Investigator assessment will be based upon institutional reports.

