**Table 5 Schedule of Assessments in Study E7080-G000-230 – Randomization Phase**

Phase	Prerandomization		Randomization a (All cycles are 21 days in duration)																		
	Screening b	Baseline c	Treatment d																Off-Tx	Follow-up	
Period	1	2	3	4	5	6	7	8	9	10	11	12	13	14	15	16	17	18+			
Visit			Cycle 1			Cycle 2			Cycle 3			Cycle 4			Cycle 5				Cycle 6-X		
Cycle			1	8	15	1	8	15	1	8	15	1	8	15	1	8	15	1			
Day	-28 to -2	-1																			
Procedures/Assessments																					

- h. Assessments will include vital signs (resting BP, HR, RR, and body temperature) and weight. Blood pressure that is consistently above the 95th percentile for sex, age, and height/length for subjects <18 years old; or BP  $\geq$ 140/90 mmHg for subjects  $\geq$ 18 to 25 years old requires further evaluation. Refer to hypertension management guidelines in [Section 9.4.1.1.2](#).
- i. On Cycle 1 Day 8, subjects will have a telephone or clinic visit to assess for the development of early toxicity. Subjects will be provided with a BP cuff to monitor BP at home or can have the measurement done by a local healthcare provider, and will report the C1D8 measurement at telephone contact. An unscheduled visit can occur prior to C1D15 if deemed necessary by the investigator.
- j. Single 12-lead ECG. If possible, subjects must be in the recumbent position for a period of 5 minutes prior to the ECG. ECG should be conducted at Screening, C1D1, C2D1, D1 of every 4th cycle (ie, C6, C10, C14, etc.). ECG at C1D1 and C2D1 should be conducted approximately 2 hours after lenvatinib dose. For high risk subjects (as defined in lenvatinib product label), conduct ECG in every cycle.
- k. An echocardiogram or MUGA scan is to be performed during screening, every 16 $\pm$ 2 weeks, and at the Off-Treatment visit, or sooner if clinically indicated.

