- b. Subjects should meet all of the safety parameters listed in the inclusion criteria and none of the safety parameters listed in the exclusion criteria. If required locally, written informed consent will be obtained prior to assessment for Optional Lenvatinib Crossover treatment.
- c. A Lansky play score or Karnofsky performance status score will be obtained at Baseline, Day 1 of every cycle, and at the Off-treatment visit.
- d. A comprehensive physical examination (including a neurological examination) will be performed at Baseline, C1D15, C2D1, C2D15, Day 1 of each subsequent cycle, and at the Off-treatment Visit. A symptom-directed physical examination will be performed on C1D1 and at any time during the study, as clinically indicated.
- e. Assessments will include vital signs (resting BP, HR, RR, and body temperature) and weight. Blood pressure that is consistently above the 95th percentile for sex, age, and height/length for subjects <18 years old; or BP  $\geq$ 140/90 mmHg for subjects  $\geq$ 18 to 25 years old requires further evaluation. Refer to hypertension management guidelines in [Section 9.4.1.1.2](#).
- f. On Cycle 1 Day 8, subjects will have a telephone or clinic visit to assess for the development of early toxicity. Subjects will be provided with a BP cuff to monitor BP at home or can have the measurement done by a local healthcare provider, and will report the C1D8 measurement at telephone contact. An unscheduled visit can occur prior to C1D15 if deemed necessary by the investigator.
- g. Single 12-lead ECG. Baseline ECG may be performed within 28 days prior to C1D1. If possible, subjects must be in the recumbent position for a period of 5 minutes prior to the ECG. ECG should be conducted at C1D1, C2D1, D1 of every 4th cycle (i.e., C6, C10, C14, etc.), and at the Off-treatment visit. For high risk subjects (as defined in lenvatinib product label), conduct ECG in every cycle.
- h. An echocardiogram or MUGA scan is to be performed at Baseline, every 16 $\pm$ 2 weeks following first dose of study drug, and at the Off-Treatment visit, or sooner if clinically indicated. The Baseline ECHO/MUGA may be performed within 28 days prior to C1D1.

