Section 9.5.2, Table 7, Schedule of Assessments (Extension Phase)	Extension phase: Study assessments are reduced in number and frequency following the completion of the PFS-1y and OS-1y analysis (ie, at the end of the Randomization phase) to reduce patient burden and risk; tumor assessments are performed in accordance with local standard of care, while ECG, echocardiograms, sampling for PK and PD analysis, and HRQoL assessments will not be required.
Section 9.5.1.4.3 Laboratory Measurements: Maximum Puncture Attempts. Maximum Blood Volume Sampling.	For children requiring venipuncture, if the practitioner is unsuccessful after two attempts, it is recommended that another suitably trained professional perform venipuncture while assessing the child's coping skills. A maximum of 3 attempts may be considered; however, clinical need and risk/benefit of further attempts should be assessed at the discretion of the investigator  The maximum volume of blood to be collected is 5% of the total blood volume over a 30-day period ( Howie, et al 2010 , Children's Memorial Research Center (CMRC), 2006 ).
Section 9.5.1.3.1: Pharmacokinetic	In order to ensure subject safety and not exceed the maximum allowable volume for blood collections,

Assessments; Table 6, Schedule of Assessments	pharmacokinetic (PK) sampling should not be performed for any subject with a body weight less than 13 kg
Section 9.5.1.3.2: Pharmacodynamic and other Biomarker Assessments; Table 5, Schedule of Assessments	In order to ensure subject safety and not exceed the maximum allowable volume for blood collections, pharmacodynamic sampling should not be performed for any subject with a body weight less than 16 kg  Furthermore, to reduce subject burden, blood sampling for pharmacodynamic biomarker assessment is optional for all subjects and will not impact eligibility.
Section 9.5.2, Table 5, Schedule of Assessments (Randomization Phase): Footnote w	Providing archival tumor samples is optional to minimize subject burden and does not impact eligibility.
Section 9.7.3 Interim Analysis	Periodic safety monitoring will be conducted by the independent data monitoring committee (IDMC) to further mitigate subject risk.

Additional changes for sites in Germany:

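### For Arm A subjects still on lenvatinib in the Extension Phase, Table 6 does not match the body text on LVEF scans and omits the every-cycle ECG for high-risk subjects

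*Protocol*

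**What the plan says.** **LVEF.** Section 9.5.1.4.7 of the protocol sets an echocardiogram or MUGA scan at screening and every 16±2 weeks from first dose, "while the subject is on treatment or sooner, if clinically indicated, and at (or within 1 week following) the off-treatment assessment". It names no phase. Table 6, the Extension Phase schedule, gives no interval and no off-treatment scan: "An echocardiogram or MUGA scan is to be performed as clinically indicated" (footnote g).

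**ECG.** Section 9.5.1.4.6 says: "Monitor ECGs every cycle (as specified in the Schedule of Assessments) in participants with congenital long QT syndrome". It extends this to congestive heart failure, bradyarrhythmias and QT-prolonging co-medication. Table 5 footnote j carries the rule for the Randomization Phase: "For high risk subjects (as defined in lenvatinib product label), conduct ECG in every cycle". Table 7 footnote g repeats it for crossover. The Table 6 row gives ECG only when clinically indicated, and its footnote f covers technique alone: "Single 12-lead ECG. Subjects must be in the recumbent position for a period of 5 minutes prior to the ECG".

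**Exposure.** Section 9.1.3.1 and Table 6 footnote j keep Arm A subjects on lenvatinib in the Extension Phase until progression, unacceptable toxicity or withdrawal. Section 9.4.1.1.11 remains the dosing rule: "Lenvatinib should be withheld in the event of development of QT interval prolongation greater than 500 msec".

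**Germany.** The Extension Phase row of Appendix Table 11-1 says "ECG, echocardiograms, sampling for PK and PD analysis, and HRQoL assessments will not be required".

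**The concern.** The cutoff that opens the Extension Phase is an analysis trigger. It changes neither a subject's drug nor the subject's cardiac risk. A site working from Table 6 would stop scheduled LVEF scans, omit the off-treatment scan and have no every-cycle ECG prompt for a high-risk subject. A site working from the body text would do all three. Both could say they followed the protocol.

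Two things are at stake. First, the QT withholding rule can act only if an ECG is taken, and the protocol itself notes that QTc prolongation has been seen with lenvatinib. In the Extension Phase that rule loses its scheduled trigger in the very subjects the protocol singles out. Second, LVEF is a listed safety variable (Section 9.7.1.8), so late and off-treatment values could be present or absent by site habit.

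**Working it through.** **Side by side, for an Arm A subject on lenvatinib after the cutoff**

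| Item | Body text | Table 6 | Table 7 (crossover) |
|---|---|---|---|
| LVEF on treatment | every 16±2 weeks (9.5.1.4.7) | if clinically indicated | every 16±2 weeks |
| LVEF at off-treatment | required (9.5.1.4.7) | no separate requirement | required |
| Routine ECG, all subjects | left to the schedule (9.5.1.4.6) | if clinically indicated | scheduled |
| ECG, high-risk subjects | every cycle, citing the schedule (9.5.1.4.6) | rule absent | every cycle |

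The LVEF rows conflict, because Section 9.5.1.4.7 sets its own interval and does not defer to a table. The routine ECG row does not conflict, because the body text defers to the schedule. The high-risk ECG row is a broken reference: the body text points to an entry that Table 6 lacks. Table 7 footnote h keeps the LVEF scan "weeks following first dose of study drug, and at the Off-Treatment visit, or sooner if clinically indicated".

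**How many subjects.** The plan gives no figure to reproduce.

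Inputs from Section 9.7.2: median PFS 8.75 months (Arm A) and 3.5 months (Arm B), 20-month enrolment, 38 events, analysis expected near month 32. The 36 subjects per arm are in Section 9.3. Assumptions: exponential PFS, uniform accrual, and dropout D of 0, 20 or 40% at 12 months, since the protocol attaches no period to its 40%.

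Dropout hazard is −ln(1−D)/12 = 0, 0.0186, 0.0426 per month. With λ = ln2/median, h = λ + dropout hazard, which for Arm A is 0.0792, 0.0978, 0.1218.

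*Event-driven cutoff.* For t up to 20 months, expected events per arm = (36/20)(λ/h)[t − (1 − e^(−ht))/h]. Setting the two-arm sum to 38 gives t = 17.8, 18.7, 19.9 months. Arm A subjects event-free and in follow-up = (36/20)(1 − e^(−ht))/h = 17.2, 15.4, 13.5. Subjects randomized after that date are not counted.

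*Cutoff at month 32.* 36[e^(−12h) − e^(−32h)]/(20h) = 7.0, 4.9, 3.1. The same inputs give about 64, 58 and 51 events by month 32, well past 38.

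*Assessments per subject.* Mean further time 1/h = 12.6, 10.2, 8.2 months. At 112 days (3.68 months) per scan this is 3.43, 2.78, 2.23 LVEF scans each. At 21 days per cycle it is 18.3, 14.8, 11.9 every-cycle ECGs for each high-risk subject.

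| Dropout at 12 months | 0% | 20% | 40% |
|---|---|---|---|
| Scheduled LVEF scans in total, cutoff at 38 events | 58.9 | 42.9 | 30.1 |
| Scheduled LVEF scans in total, cutoff at month 32 | 24.0 | 13.6 | 7.0 |

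Each subject would also have one off-treatment scan under the body text.

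**The case against.** The best defence is that each phase has its own schedule. Sections 9.5.2.1 and 9.5.2.2 assign Table 6 to the Extension Phase, and Section 9.5.1.4 says ECGs and echocardiograms follow Tables 5 and 6. On this view Section 9.5.1.4.7 merely repeats the Table 5 interval without its phase. The reduction also looks deliberate: Appendix 11 describes assessments being cut back over time, and in the Extension Phase, to spare subjects burden. Much of this stands. Table 6 is a plausible governing document, and restoring 16-weekly scans is a trade-off the sponsor may decline. But no text gives the tables precedence or ends the Section 9.5.1.4.7 rule at the cutoff, and this defence cannot supply the ECG entry that Section 9.5.1.4.6 cites.

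A reader might infer three competing rules by counting the German row. The documents do not support that: saying scans are not required is close to saying they are done when clinically indicated, so there are two rules. A reader might also infer that Table 6 forbids ECGs in high-risk subjects. It does not. A named risk factor can be a clinical indication, and exclusion criteria 8 and 9 remove some such subjects at entry. What is lost is the scheduled prompt.

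Nor is the contrast with Table 7 an error in itself. Crossover subjects are starting lenvatinib, whereas Arm A subjects have already been monitored on it under Table 5. Table 7 shows only that the high-risk rule was carried into another lenvatinib schedule.

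**Conclusion.** The point holds, at minor severity. There is one direct conflict (LVEF interval and off-treatment scan) and one omission (high-risk every-cycle ECG), both for Arm A subjects who continue lenvatinib in the Extension Phase at any site. The omission matters more, because it removes the scheduled trigger for a dose-withholding rule.

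The size depends on the cutoff date: about 13 to 17 subjects and 30 to 59 scheduled LVEF scans if 38 events arrive near months 18 to 20, or about 3 to 7 subjects and 7 to 24 scans at month 32. The month-32 range should not be read as a ceiling, since the cutoff is set by events and the planning medians put it earlier. These counts are of subjects event-free and in follow-up. Fewer would be on lenvatinib, because stopping for toxicity is not modelled. The high-risk share is not given, so the total number of ECGs cannot be stated. The primary endpoint, alpha and power are unaffected.

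**What to change.** 1. Add to Table 6 footnote f the sentence already in Tables 5 and 7: "For high risk subjects (as defined in lenvatinib product label), conduct ECG in every cycle".
2. Settle LVEF one way. Either carry the Section 9.5.1.4.7 rule into Table 6 footnote g, at least the off-treatment scan, or, if the burden reduction in Appendix 11 is intended, limit Section 9.5.1.4.7 to the Randomization and Crossover Phases.
3. Align the Extension Phase row of Appendix Table 11-1 with the choice. As an editorial matter, correct its reference to the PFS-1y and OS-1y analysis, its table number, and its statement on HRQoL, which Table 6 footnote o does collect.

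The cost is two footnotes (or one footnote and one sentence) and one appendix row at the next amendment. The added procedures are every-cycle ECGs in high-risk subjects only and, if kept, the LVEF scans counted above. The body text already requires both.
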